2.2 Study description

The study is expected to be conducted at approximately 100 study sites globally with approximately 2,300 subjects contributing to total enrollment numbers. Participating geographies are expected to include, but are not limited to: the United States, Europe Middle East and Africa (EMEA), China and Japan. Subjects will be followed for 3 years or until study closure which is expected to be in January of 2021.

To ensure a widespread distribution of data and minimize site bias in study results, the maximum number of subjects who may have a Reveal LINQ inserted at a single site is recommended to be fifteen percent (15%) of total projected enrollment in a given geography based on enrollment allocations. Sites that enroll faster than others will be allowed to do so in order to maintain an adequate overall study enrollment rate, but may not exceed the maximum number of insertions per site.

All subjects will be followed in-office in accordance with standard care practices of their respective care provider. Follow-up data collection is required at minimum every 6 months post-insertion and real time reporting is required for arrhythmia events and actions taken as a result of the Reveal LINQ ICM. This data may be collected via in-office subject clinic visit, remote monitor transmissions review, or chart review. Subjects are followed until subject death or exit, the implanted device becomes inactive or explanted, the subject has been followed for 3 years, or study closure which is expected to be in January of 2021.

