6.1.3. Analysis Sets

A set of analysis datasets will be created based on forms (enrolled, procedure, follow-up (including deaths & exits), atrial fibrillation (AF) ablation, events, deviations). A flagging variable will indicate whether or not subject was enrolled prior to LINQ product insertion procedure.

Only subjects enrolled prior to LINQ insertion will be used in safety analyses of procedure-related adverse events and will comprise the Safety Analysis Set. For all other analyses, any study subjects may be used, comprising the Full Analysis Set.

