6.4. Handling of Missing Data and Dropouts

Missing data imputation methods will not be used for the study objectives unless specified otherwise within the analysis methods.

As reflected in specific analysis methods below, any analyses related to infections could be biased by the fact that in prior versions of the protocol, subjects were allowed to be enrolled up to 30 days post insertion. Subjects who had an early infection (especially if it lead to an early explant) may have been less likely to have enrolled post-procedure. Thus, subjects enrolled after day of insertion will not be included in analyses of procedure-related adverse events.

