6.9. Evaluation of Objectives

Primary Objective #1

Characterize clinical actions initiated by Reveal LINQ arrhythmia detection.

i. Analysis Methods

This objective is descriptive in nature. New onset of arrhythmias diagnosed as results of ICM data review, and the subsequent clinical actions taken are reported through CRFs.

Study sites will review device recorded arrhythmia episodes via remote transmission or at a regularly scheduled clinic visit. Clinical treatments may be prescribed upon diagnosis.

Summary statistics will be obtained for frequencies of diagnosis and treatment. Frequencies of each action taken, such as medication changes, surgical intervention, new cardiac device implant, etc. will be obtained.

Endpoint definition: First incidence of onset of new arrhythmias for each type diagnosed as result of ICM data review during the study, regardless of whether or not the patient had arrhythmias also reported in their medical history. The subsequent clinical actions taken are reported through Follow-up CRFs.

Follow-up CRF question 9) "Were any new diagnoses made as a result of review of ICM data during this visit" where arrhythmia type is selected, considering only the *first* diagnosis of each type for the subject and linking to Treatment log "Treatment Type" with Treatment Trigger checked as being "Monitor Data" and where treatment date is on or after first diagnosis of event.

Example output shell:

Arrhythmia type	Number of patients (%)
Atrial Fibrillation	N (%)
Bradycardia	N (%)
Tachycardia	N (%)
Overall total	N (%)

Atrial Fibrillation	N (%)									
Bradycardia	N (%)									
Tachycardia	N (%)									
Overall total	N (%)									

Additional analysis

An additional sensitivity analysis will be performed to account for the follow-up time of subjects in study and characterize the incidence of first arrhythmias and actions taken by arrhythmia type. This sensitivity analysis will be done to account for potential differences in reporting for those subjects enrolled after insertion who may not have fully reported actions taken between insertion and consent.

ii. Determination of Subjects/Data for Analysis

Any enrolled subjects who are diagnosed with an arrhythmia detected by Reveal LINQ will be included in analysis.

iii. Sample Size

There is no statistical hypothesis formulated for this analysis therefore there is no sample size for this objective.

Primary Objective #2

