6.12. Changes to Planned Analysis

Changes and clarifications to planned analysis from CIP are as noted.

Primary objective 1:

- Clarified only consider *first* incidence of onset of new arrhythmia during the study *regardless of* whether or not subject has *history* of incidence.

- Added a sensitivity analysis that considers follow-up time. This is to account for possibility of missed reporting of actions taken for subjects who enrolled after insertion.

Primary objective 2:

- Clarified “Determination of Subjects” so that subject *must have enrolled in the study prior to implant and* met one of the four (A-D) criteria. CIP only requires consent for subjects in bullet A, and does not require that consent be given *prior* to insertion.
- Added a sensitivity analysis using Wilson interval, since infection rates may be quite small.

Ancillary objective 1**Ancillary objective 2****Ancillary objective 4**

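### Adjusting Objective 1 for follow-up time does not by itself correct for actions unreported before consent in late enrollees; specify delayed entry and repeat the analysis in subjects enrolled before insertion

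*SAP*

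**What the plan says.** SAP 6.4 records that under prior protocol versions "subjects were allowed to be enrolled up to 30 days post insertion". Because of this, it removes late enrollees from analyses of procedure-related adverse events, and SAP 6.1.3 creates a flag for enrolment before insertion.

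Objective 1 keeps these subjects: "For all other analyses, any study subjects may be used, comprising the Full Analysis Set". The endpoint takes diagnoses from the follow-up form, "considering only the *first* diagnosis of each type for the subject", and links monitor-triggered treatments "where treatment date is on or after first diagnosis of event". The main output is a count and percentage by arrhythmia type.

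SAP 6.9 then adds: "An additional sensitivity analysis will be performed to account for the follow-up time of subjects in study". The follow-up-time analysis is added because of "those subjects enrolled after insertion who may not have fully reported actions taken between insertion and consent". SAP 6.12 gives the same reason: "This is to account for possibility of missed reporting of actions taken for subjects who enrolled after insertion". Neither section names an estimator, a time origin, a rule for entry to the risk set, or the handling of a diagnosis made before consent. The Objective 1 text does not use the flag. Follow-up lasts 3 years or until "study closure which is expected to be in January of 2021" (Protocol 2.2).

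**The concern.** The stated problem is missing reports in a window of up to 30 days. The stated remedy changes the denominator. Three things can go wrong.

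- Time from insertion, no delayed entry: a late enrollee contributes days in which events may not have been recorded, and these count as event-free.
- Time from consent: the unrecorded days leave the denominator, but so does the early period itself. The rate is right only if detection is as frequent then as later.
- Endpoint rules: if an early diagnosis goes unreported, the next recorded one of that type becomes the first, and treatments dated before it are not linked. This touches clinical actions, the subject of the objective.

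This is the only safeguard planned for a bias in a primary objective that the SAP itself identifies. Left unspecified, it could be run in a form that keeps most of the bias and then be cited as reassurance.

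**Working it through.** Objective 1 states no rate, event count or sample size, so there is no figure in the plan to reproduce.

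**Inputs from the documents.** Late-enrolment window 30 days (SAP 6.4); follow-up 1096 days (Protocol 7.9.5).

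**Assumed inputs, not in the documents.** True 3-year incidence of first diagnosis I3 = 15% or 30%; hazard in days 0–30 equal to r = 1, 3 or 10 times the later hazard; share enrolled late f = 25% or 50%, with consent uniform over days 0–30; pre-consent diagnoses never reported; 20% attrition over 3 years.

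**Step 1: 30-day incidence.** I30 = 1 − (1 − I3)^(30r / (1066 + 30r)). For I3 = 30% and r = 3: 1 − 0.7^(90/1156) = 2.74%.

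**Step 2: share missed.** With consent uniform over the window, about half of a late enrollee's 30-day diagnoses fall before consent, so the missed share is about f × I30 / 2. The relative loss at 30 days is about f/2: 12.5% for f = 25% and 25% for f = 50%.

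**Step 3: simulation, 2,000,000 subjects per scenario.** Losses are for Kaplan-Meier (KM) from insertion without delayed entry.

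| I3 | r | f | I30 | f × I30 / 2 | Simulated share missed | KM at 3 years | Loss at 3 years (points) |
|---|---|---|---|---|---|---|---|
| 15% | 1 | 25% | 0.44% | 0.055% | 0.055% | 14.97% | 0.03 |
| 15% | 10 | 50% | 3.51% | 0.88% | 0.891% | 14.13% | 0.87 |
| 30% | 1 | 50% | 0.97% | 0.24% | 0.237% | 29.77% | 0.23 |
| 30% | 3 | 50% | 2.74% | 0.69% | 0.680% | 29.25% | 0.75 |
| 30% | 10 | 50% | 7.53% | 1.88% | 1.894% | 28.06% | 1.94 |

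The standard error of a simulated 15% is about √(0.15 × 0.85 / 2,000,000) = 0.025 points, so 0.03 is at the level of simulation noise.

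**Step 4: person-time rates** per 100 patient-years (I3 = 30%, f = 50%).

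| r | All reported | From insertion | From consent |
|---|---|---|---|
| 1 | 11.88 | 11.75 | 11.85 |
| 3 | 12.04 | 11.65 | 11.75 |
| 10 | 12.60 | 11.47 | 11.57 |

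At r = 10 the rates are low by 1 − 11.47/12.60 = 9.0% and 1 − 11.57/12.60 = 8.2%. At r = 1, time from consent is nearly right.

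**Step 5: alternatives** (I3 = 30%, f = 50%), cumulative incidence in %.

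| Estimator | r = 3, 3 years | r = 3, 30 days | r = 10, 3 years | r = 10, 30 days |
|---|---|---|---|---|
| Truth | 30.0 | 2.74 | 30.0 | 7.53 |
| KM from insertion, no delayed entry | 29.25 | 2.04 | 28.06 | 5.62 |
| KM from consent | 29.41 | 2.27 | 28.20 | 5.80 |
| KM from insertion, delayed entry at consent | 29.72 | 2.68 | 29.41 | 7.39 |
| As above, excluding known pre-consent diagnoses | 29.91 | 2.69 | 29.90 | 7.44 |
| Enrolled before insertion only | 29.95 | 2.73 | 29.96 | 7.52 |

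Delayed entry removes most of the bias, and restriction removes essentially all of it.

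**The case against.** The strongest reply is that the SAP leaves a detail open and makes no error. Follow-up in the study most naturally starts at consent, because SAP section 5 treats signing as enrolment. On that reading no unreported day counts as event-free, and with a constant detection rate the answer is nearly unbiased (11.85 against 11.88). Protocol 2.2 also allows chart review and review of remote transmissions, so pre-consent information need not be lost. The objective is descriptive, and late enrolment is a legacy of earlier protocol versions.

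Much of this stands and limits the importance of the point. It does not remove it. Nothing in the documents supports a constant rate. The endpoint counts first detection whatever the arrhythmia history, and Protocol section 3 describes use after AF ablation, so early detections are plausible, though no rate is given.

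A reader might infer four stronger things that the documents do not support.

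- *That no follow-up-time analysis could correct the bias.* Delayed entry corrects most of it, and the SAP neither specifies nor excludes that method.
- *That early diagnoses are left-truncated.* Late enrollees are in the sample with early reports possibly missing. Selection out of enrolment is described only for infections (SAP 6.4). The SAP names unreported actions; unreported diagnoses are an inference.
- *That the loss could reach several points.* Multiplying, for example, 20–60% late enrolment by 3–10% diagnosed before consent gives 0.6 to 6.0 points. Neither factor is in the documents, and the product treats every early diagnosis as lost for good, although a repeat detection would put the subject back in the 3-year percentage.
- *That the crude main table is a separate fault because follow-up is unequal.* Accounting for follow-up time is what the added analysis is for.

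**Conclusion.** The point holds as a mismatch between the stated purpose and an under-specified method. Adjusting for follow-up time does not by itself deal with missed reporting between insertion and consent, and the two simple versions leave bias unless the time origin is consent and the detection rate is constant.

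The size cannot be known from the documents. Under the assumed inputs the loss at 3 years without delayed entry is about 0.03 to 0.9 points for a true incidence of 15%, and about 0.1 to 1.9 points for 30%. The upper end needs half the subjects enrolled late and a tenfold early hazard. These figures also assume that no pre-consent diagnosis is ever reported, so fuller reporting would shrink them. The effect is mainly on 30-day figures, with a relative loss of about 11–13% at 25% late enrolment and about 25% at 50%. The loss of linked treatments was not quantified. No hypothesis test is affected.

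**What to change.** In SAP 6.9, Objective 1:

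1. Repeat the diagnosis and action summaries in subjects enrolled before insertion, using the flag in 6.1.3. This parallels what 6.4 already does for procedure-related events and needs no assumption about the early detection rate.
2. Define the follow-up-time analysis as time from insertion to first recorded diagnosis of each type, with delayed entry at the later of insertion and consent, ending at death, explant, exit or closure. State that undiagnosed subjects are in the risk set.
3. Do not remove subjects diagnosed before consent unless those dates are recorded. The documents do not show that they are. Removal would also treat that history differently from other arrhythmia history, which the endpoint disregards.

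The change is a few sentences of SAP text, with no new visits. The cost is precision in the restricted analysis: standard errors grow by 1/√0.75 = 1.15 if 25% enrolled late and by 1/√0.5 = 1.41 if 50% did. The main Objective 1 table is unchanged.

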6.10. Safety Evaluation

Adverse events will be summarized by relatedness (procedure & component (ICM, insertion tool, incision tool, other)), seriousness, and event primary diagnosis.

6.11. Health Outcomes Analyses

No health outcomes analyses are planned as part of this study.

6.12. Changes to Planned Analysis

Changes and clarifications to planned analysis from CIP are as noted.

Primary objective 1:

- Clarified only consider *first* incidence of onset of new arrhythmia during the study *regardless of* whether or not subject has *history* of incidence.

- Added a sensitivity analysis that considers follow-up time. This is to account for possibility of missed reporting of actions taken for subjects who enrolled after insertion.

Primary objective 2:

- Clarified “Determination of Subjects” so that subject *must have enrolled in the study prior to implant and* met one of the four (A-D) criteria. CIP only requires consent for subjects in bullet A, and does not require that consent be given *prior* to insertion.
- Added a sensitivity analysis using Wilson interval, since infection rates may be quite small.

Ancillary objective 1**Ancillary objective 2****Ancillary objective 4**

6.13. Handling of non-CRF data

This study will collect the results of diagnostic imaging (for e.g. EKG, CT scan) conducted for subjects from the sites when available. These images are not part of the CRF data collection. Images will be sent to the study via Clinical Transfer and stored in a designated shared drive. CareLink will store device data that is uploaded from the device. For statistical analysis of study objectives, these data will not be used. However, these files may be reviewed for data completeness and data quality.

7. Validation Requirements

All analysis of primary objectives will have level I validation.

All analysis of ancillary objectives will require level II (or better) validation.

8. References

N/A
